9.1.1 Multiplicity Adjustment

Not applicable

9.2 Analysis Sets

Efficacy, safety, will be summarized for the ITT population.

Participant Analysis Set	Description
Intent-to-treat population (ITT)	All participants enrolled in the study

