To assess onset of effect of VTAMA (tapinarof) cream, 1% in adults with intertriginous PSO	 Time to achieve an iPGA score of 0 or 1 with a ≥ 2-grade improvement from Baseline

Overall Design Synopsis:

Brief Summary:

The purpose of this open-label study is to evaluate the efficacy and safety of VTAMA (tapinarof) cream, 1% in adults with intertriginous PSO. Efficacy of the treatment of plaque PSO in intertriginous areas will be assessed with a PGA evaluation only of intertriginous areas (iPGA).

Participants will be allowed

to treat plaque PSO in other body areas according to instructions provided in USPI, but no assessments of efficacy will be performed outside of intertriginous

VTAMA will be dispensed and will be administered at home between clinic visits as instructed by site personnel. Application instructions will be reviewed at all clinic visits except during the final treatment/end-of-study visits. Participants will be instructed to apply cream QD to all affected areas, including intertriginous areas, and any other locations on the body. Existing lesions will be treated as well as newly appearing lesions and lesions/areas that improved or cleared during the study. Participants will apply sufficient cream to cover completely each lesion with a thin layer and will record the time of application in a daily diary provided by the study site. Participants will be instructed to maintain the approximate dosing time chosen at the beginning of the study for their full study participation.

Number of Participants:

Approximately 30 participants will be enrolled.

Note: Enrolled means participants agreement to participate in a clinical study following completion of the informed consent process and screening. Potential participants who are screened for the purpose of determining eligibility for the study, but do not participate in the study, are not considered enrolled, unless otherwise specified by the protocol. A participant will be considered enrolled if the informed consent is not withdrawn prior to participating in any study activity after screening.

Study Arms and Duration:

VTAMA (tapinarof) cream, 1% is a white to off-white cream containing 1% weight/weight (10 mg/g) tapinarof, supplied in 60-gram tubes. VTAMA is to be administered by the participant QD via topical application of a thin layer to affected areas in accordance with instructions in USPI.

Dosing may be interrupted if deemed necessary by the Investigator for management of adverse events.

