5.1 Inclusion Criteria

Participants are eligible to be included in the study only if all of the following criteria apply:

Age

1. Participant must be 18 years of age or older, at the time of signing the informed consent.

Type of Participant and Disease Characteristics

- 2. Participants with clinical diagnosis of plaque PSO, including lesion(s) in intertriginous area(s) and stable disease in intertriginous areas for at least 3 months prior to the study
- 3. An iPGA score of 2 (mild), 3 (moderate), or 4 (severe) at screening and baseline.

Sex and Contraceptive/Barrier Requirements

Contraceptive use by men and women should be consistent with local regulations regarding the methods of contraception for those participating in clinical studies.

4. Female participants:

A female participant is eligible to participate if she is not pregnant or breastfeeding, and one of the following conditions applies:

- Is a WONCBP as defined in Appendix 4 Contraceptive and Barrier Guidance OR
- Is a WOCBP and using an acceptable contraceptive method as described in Appendix 4 Contraceptive and Barrier Guidance during the treatment period, until after the last dose of study product. The Investigator should evaluate the potential for contraceptive method failure (e.g., noncompliance, recently initiated) in relationship to the first dose of study product).
 - A WOCBP must have a negative urine pregnancy test before the first dose of study product, see Section 8.3.1 Pregnancy Testing.
 - The Investigator is responsible for review of medical history, menstrual history, and recent sexual activity to decrease the risk for inclusion of a woman with an early undetected pregnancy.

Informed Consent

5. Capable of giving signed informed consent as described in Appendix 1 which includes compliance with the requirements and restrictions listed in the ICF and in this protocol; written informed consent must be obtained prior to any study related procedures.

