# 5. STATISTICAL CONSIDERATIONS

### 5.1. General Considerations

will perform the statistical analysis of the data. SAS version 9.4 or higher will be used to generate all statistical outputs (tables, listings, figures [TLFs], and datasets). The International Council for Harmonisation (ICH) numbering convention will be used for all TLFs. Continuous endpoints will be summarized by presenting the number of observations, means, standard deviations, medians, minimums, and maximums. The 95% confidence intervals will be reported as appropriate.

Time to event analyses will use the Kaplan-Meier product limit method (if estimable) based on observed cases.

Categorical endpoints will be summarized by presenting counts and percentages of subjects in corresponding categories. All possible categories as defined in the case report form (CRF) will be populated, even if they have zero counts. With the exception of ethnicity and race in the demographic table, percentages for missing values are omitted and do not account for the percent calculation of other categories. In certain tables (e.g., TEAEs), the total number of subjects is used as denominator. Footnotes will specify the percent basis in those cases.

Individual subject data obtained from the eCRFs and any derived data will be presented by subject in data listings.

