### 5.2. Analysis Populations

The intent-to-treat (ITT) population will include all participants enrolled in the study.

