# 8.2. Adverse Events

All AE summaries will be restricted to TEAEs, which are defined as those AEs that occurred after dosing and those pre-existing AEs (prior to first application of study treatment) that worsened during the study. If it cannot be determined whether the AE is treatment emergent due to a partial onset date, then it will be counted as TEAE. Verbatim terms in the eCRFs will be mapped to SOCs and PTs using MedDRA (Version 26.0).

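### Safety is summarised on everyone enrolled and no dosed population is defined, so any enrolled participant who never applied the cream would lower the TEAE percentages (minor)

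*Protocol*

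**What the plan says.** **Analysis set.** Protocol 9.2 states: "Efficacy, safety, will be summarized for the ITT population". It defines that population as "All participants enrolled in the study". SAP 5.2 agrees and names no other set: "The intent-to-treat (ITT) population will include all participants enrolled in the study".

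**Denominator.** SAP 5.1 says: "In certain tables (e.g., TEAEs), the total number of subjects is used as denominator". The next sentence promises footnotes giving the basis of the percentage.

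**Numerator.** SAP 8.2 restricts AE summaries to TEAEs, "which are defined as those AEs that occurred after dosing", together with pre-existing events that worsened during the study.

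**Enrolment.** The note under Number of Participants in Protocol 1.1 reads: "Enrolled means participants agreement to participate in a clinical study following completion of the informed consent process and screening". It ends: "A participant will be considered enrolled if the informed consent is not withdrawn prior to participating in any study activity after screening". Neither sentence mentions a dose. Protocol 6.2 allows study product to be given only to people already enrolled, so the dosed are a subset of the enrolled.

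**First dose.** Protocol 6.5 has the first application made under supervision at Visit 2. SAP 8.1 calls it the in-clinic dose at Baseline.

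**The concern.** The TEAE numerator depends on exposure and the denominator does not. Someone who is enrolled and leaves before the first application adds one to the denominator of every TEAE table with almost no chance of adding to a numerator. The error runs one way, towards lower event rates. The study has a single arm, so no comparator would carry the same dilution.

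The plan's other safety rules also do not fit such a person:

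- Study day (SAP 5.3) and baseline value (SAP 6.4) are both defined from the first dose.
- Days exposed (SAP 8.1) cannot be calculated, so compliance cannot be either. SAP 8.1 then assumes less than 80% compliance, and a person who never started treatment is reported as non-compliant.
- Disposition (SAP 6.1) counts the screened, the ITT population, completers and reasons for discontinuation, but not the number dosed. That table would not show whether ITT and dosed differ.

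**Working it through.** **1. Is there a figure to reproduce?** No. The planned 30 rests on clinical considerations without a calculation (Protocol 9.5, SAP 4). Neither document gives an expected TEAE rate or a number enrolled but undosed. The event counts and undosed counts below are assumptions, used only for scale.

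**2. Can an enrolled participant go undosed?** Some requirements fall between screening and the first application:

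- Protocol 5.1 requires "An iPGA score of 2 (mild), 3 (moderate), or 4 (severe) at screening and baseline", so severity is checked twice.
- Protocol 5.2 counts medication wash-outs and UV exposure back from the Baseline visit.
- Protocol 5.1 requires a negative urine pregnancy test ahead of the first dose in women of childbearing potential.
- The stated durations leave up to 17 − 12 − 1 = 4 weeks outside treatment and follow-up, in which disease severity can change.

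A person who starts Visit 2 and then fails a check or withdraws could meet the last sentence of the enrolment note. Against that, the same note excludes people screened for eligibility who do not go on to participate, and Protocol 5.4 treats a consented person not entered in the study as a screen failure. The texts do not settle which applies. The schedule of activities is not in the text available for this review, so the order of Visit 2 procedures could not be checked.

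**3. Size of the dilution.** Let N = 30 be enrolled, k of them undosed, and x participants have a given TEAE, all of them dosed.

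- Reported rate: x / 30
- Rate among the exposed: x / (30 − k)
- Ratio of the two: (30 − k) / 30, a relative understatement of k / 30

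Each cell shows the rate on the enrolled, then on the dosed:

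| k | Dosed | Ratio | x = 3 | x = 6 | x = 15 |
|---|---|---|---|---|---|
| 0 | 30 | 1.000 | 10.0%, 10.0% | 20.0%, 20.0% | 50.0%, 50.0% |
| 1 | 29 | 0.967 | 10.0%, 10.3% | 20.0%, 20.7% | 50.0%, 51.7% |
| 2 | 28 | 0.933 | 10.0%, 10.7% | 20.0%, 21.4% | 50.0%, 53.6% |
| 3 | 27 | 0.900 | 10.0%, 11.1% | 20.0%, 22.2% | 50.0%, 55.6% |

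For k = 1 the largest possible gap is 3.3 percentage points, when all 29 dosed have the event (29/30 = 96.7% against 100%). A rate of 0% does not change.

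**4. Against sampling error.** The exact (Clopper-Pearson) 95% interval for 6/30 is 7.7% to 38.6%. The shift of 0.7 points for k = 1, or 2.2 points for k = 3, is small beside it.

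**5. Compliance.** One undosed person in 30 puts 1/30 = 3.3 percentage points into the below-80% class. If all 29 dosed were compliant, the table would show 96.7% instead of 100%.

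**The case against.** The strongest reply is that the case may never arise. Baseline iPGA is an inclusion criterion, and Protocol 5.4 can be read to make anyone who fails it a screen failure, outside ITT. Eligible participants then apply the cream under supervision at the same visit. Only someone who stops between the Visit 2 checks and that application would be enrolled and undosed. This stands as a limit on how likely the problem is. It does not remove it, because nothing in either document makes enrolment depend on a dose.

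The second reply is disclosure. Footnotes will state the percentage basis, and SAP 5.1 and 8.2 list subject data and AEs by subject. With about 30 participants, a reader with the listings could find an undosed person and recompute. That is fair, but a reader of the tables alone would not see the number dosed.

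Third, the numerator is not wholly closed to the undosed. A pre-existing event that worsened during the study counts under SAP 8.2, as does an event whose start date is completely missing. The compliance rule also works against the product. The one-way bias therefore applies to the TEAE percentages, and there only nearly always.

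Finally, the study is descriptive and no stated conclusion turns on a shift of this size. That stands, and it is why the point is minor.

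**Conclusion.** The gap is real and minor. Safety is summarised on all enrolled, enrolment is not tied to a dose, and the TEAE numerator largely is. Each undosed person among 30 would lower every non-zero TEAE percentage by a relative 3.3% and would be counted as non-compliant. If everyone enrolled is dosed, nothing changes. The calculation assumes exactly 30 enrolled and no TEAE recorded for an undosed person.

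A reader might infer more in three ways, and the documents support none of them:

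- **That the TEAE rates are in fact diluted.** Neither document reports or anticipates an undosed participant.
- **That a Baseline eligibility failure is certainly enrolled.** The enrolment note and Protocol 5.4 leave this open.
- **That the understatement reaches 10%.** That needs three undosed of 30, a count with no source. Nor should one argue from the upper confidence limit for an event never seen, because the AE summaries planned in SAP 8.2 are counts and percentages.

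**What to change.** The change can be made in the SAP alone:

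- **SAP 5.2:** add a safety population, defined as all enrolled participants who applied at least one dose of study product.
- **SAP section 8:** use it for exposure, compliance and the AE summaries. Keep ITT for efficacy (SAP section 7).
- **SAP 6.1:** add the number dosed to the disposition table.
- **SAP 11.1:** record this as a modification, because Protocol 9.2 assigns safety to ITT.

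Events in anyone enrolled but not dosed remain visible, since SAP 8.2 already lists all AEs by subject.

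The cost is a definition, a population flag, one disposition row and one entry in the modifications section. If every enrolled participant is dosed, the safety results are identical. Putting the same definition into Protocol 9.2 would need an amendment with the review set out in Protocol 10.1.1, and the point does not justify that by itself.

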9.3 Statistical Analyses

9.3.1 General Considerations

This study is intended to show that VTAMA (tapinarof) cream, 1% has a favorable safety and efficacy profile when applied to intertriginous areas over a 12-week dosing period.

Objectives and endpoints are provided in Section 3.

Every effort will be made to collect complete data at all visits. All efficacy data will be summarized based on OC. The primary and exploratory efficacy endpoints will also be summarized utilizing the last observation carried forward method to impute missing data

9.3.2 Primary Endpoint Analysis

The primary efficacy endpoint will be summarized descriptively with frequency count, percentage, and 95% confidence interval.

9.3.3 Secondary Endpoint Analysis

The Kaplan-Meier product limit method will be used to estimate the median time to achieving an iPGA score of 0 or 1 with a \geq 2-grade improvement from Baseline (if estimable).

9.3.4

9.3.5 Safety Analyses

The number and percent of participants with TEAEs will be summarized by system organ class, and preferred term for all TEAEs, all TEAEs by system organ class, preferred term, and maximum CTCAE grade, all TEAEs considered by the Investigator to be related to study product, SAEs, TEAEs leading to study product discontinuation, and TEAEs leading to discontinuation from study.

9.4 Interim Analysis

Not applicable

9.5 Sample Size Determination

The sample size for this study is based on clinical considerations only. No formal sample size calculation will be performed. A total of 30 participants is planned for this study which is considered adequate to evaluate the efficacy and safety for the treatment of plaque PSO in the intertriginous areas.

10 Supporting Documentation and Operational Considerations

10.1 Appendix 1: Regulatory, Ethical, and Study Oversight Considerations

10.1.1 Regulatory and Ethical Considerations

- This study will be conducted in accordance with the protocol and with the following:
 - Consensus ethical principles derived from international guidelines including the Declaration of Helsinki and Council for International Organizations of Medical Sciences international ethical guidelines
 - Applicable ICH GCP guidelines
 - Applicable laws and regulations
- The protocol, protocol amendments, ICF, Investigator's brochure, and other relevant documents (e.g., advertisements) must be submitted to an IRB/IEC by the Investigator and reviewed and approved by the IRB/IEC before the study is initiated.
- Any amendments to the protocol will require IRB/IEC approval before implementation of changes made to the study design, except for changes necessary to eliminate an immediate hazard to study participants.
- Protocols and any substantial amendments to the protocol will require health authority approval prior to initiation (if applicable per country- or region-specific regulations) except for changes necessary to eliminate an immediate hazard to study participants.
- The Investigator will be responsible for the following, as applicable:
 - Providing written summaries of the status of the study to the IRB/IEC annually or more frequently in accordance with the requirements, policies, and procedures established by the IRB/IEC
 - Notifying the IRB/IEC of SAEs or other significant safety findings as required by IRB/IEC procedures
 - Providing oversight of the conduct of the study at the site and adherence to requirements of 21 CFR, ICH guidelines, the IRB/IEC, European regulation 536/2014 for clinical studies, European Medical Device Regulation 2017/745 for clinical device research, and all other applicable local regulations

10.1.2 Financial Disclosure

Investigators and Sub-Investigators will provide the Sponsor with sufficient, accurate financial information as requested to allow the Sponsor to submit complete and accurate financial certification or disclosure statements to the appropriate regulatory authorities. Investigators and Sub-Investigators are responsible for providing information on financial interests during the course of the study and for 1 year after completion of the study.

10.1.3 Informed Consent Process

- The Investigator or the Investigator's representative will explain the nature of the study, including the risks and benefits, to the potential and answer all questions regarding the study.
- Potential participants must be informed that their participation is voluntary. Participants will be required to sign a statement of informed consent that meets the requirements of 21 CFR 50, local regulations, ICH guidelines, privacy and data protection requirements, where applicable, and the IRB/IEC or study center.
- The medical record must include a statement that written informed consent was obtained before the participant was enrolled in the study and the date the written consent was obtained. The authorized person obtaining the informed consent must also sign the ICF.

• Participants must be reconsented to the most current version of the ICF(s) during their participation in the study.

• A copy of the ICF(s) must be provided to the participant.

Participants who are rescreened are required to sign a new ICF.

10.1.4 Data Protection

- Participants will be assigned a unique identifier by the Sponsor. Any participant records or datasets that are transferred to the Sponsor will contain the identifier only; participant names or any information which would make the participant identifiable will not be transferred.
- The participant must be informed that their personal study-related data will be used by the Sponsor in accordance with local data protection law. The level of disclosure must also be explained to the participant who will be required to give consent for their data to be used as described in the informed consent
- The participant must be informed that their medical records may be examined by Clinical Quality Assurance auditors or other authorized personnel appointed by the Sponsor, by appropriate IRB/IEC members, and by inspectors from regulatory authorities.
- The contract between Sponsor and study sites specifies responsibilities of the parties related data protection, including handling of data security breaches and respective communication and cooperation of the parties.
- Information technology systems used to collect, process, and store study-related data are secured by technical and organizational security measures designed to protect such data against accidental or unlawful loss, alteration, or unauthorized disclosure or access.

10.1.5 Dissemination of Clinical Study Data

Anonymized Clinical Study Reports will be disclosed as required by regulatory authorities.

Study information and tabular study results will be posted on National Institutes of Health's website www.clinicaltrials.gov and other publicly accessible sites. Study results may be published in peer-reviewed publications or presented at scientific meetings.

Following an assessment of a rigorously defined research question from a third party, Dermavant may grant access to analyzable datasets from this study through a secure system.

10.1.6 Data Quality Assurance

- All participant data relating to the study will be recorded on printed or electronic CRFs unless transmitted to the Sponsor or designee electronically (e.g., laboratory data). The Investigator is responsible for verifying that data entries are accurate and correct by physically or electronically signing the CRF.
- Guidance on completion of CRFs will be provided in CRF completion guidelines.
- The Investigator must permit study-related monitoring, audits, IRB/IEC review, and regulatory agency inspections and provide direct access to source documents.
- Monitoring details describing strategy, including definition of study critical data items and
 processes (e.g., risk-based initiatives in operations and quality such as risk management and
 mitigation strategies and analytical risk-based monitoring), methods, responsibilities, and
 requirements, including handling of noncompliance issues and monitoring techniques (central,
 remote, or on-site monitoring) are provided in the Study Reference Manual.
- The Sponsor or designee is responsible for the data management of this study, including quality checking of the data.

• The Sponsor assumes accountability for actions delegated to other individuals (e.g., contract research organizations).

• Records and documents, including signed ICFs, pertaining to the conduct of this study must be retained by the Investigator for 15 years after study completion unless local regulations or institutional policies require a longer retention period. No records may be destroyed during the retention period without the written approval of the Sponsor. No records may be transferred to another location or party without written notification to the Sponsor.

10.1.7 Source Documents

- Source documents provide evidence for the existence of the participant and substantiate the integrity of the data collected. Source documents are filed at the Investigator's site.
- Data reported on the CRF or entered in the eCRF that are transcribed from source documents must be consistent with the source documents or the discrepancies must be explained. The Investigator may need to request previous medical records or transfer records, depending on the study. Also, current medical records must be available.
- Definition of what constitutes source data and its origin can be found in source data acknowledgment.
- The Investigator must maintain accurate documentation (source data) that supports the information entered in the eCRF.
- The Sponsor or designee will perform monitoring to confirm that data entered into the CRF by authorized site personnel are accurate, complete, and verifiable from source documents; that the safety and rights of participants are being protected; and that the study is being conducted in accordance with the currently approved protocol and any other study agreements, ICH GCP, and all applicable regulatory requirements.

